13.4 Sample Receipt/Chain of Custody/Accountability

Samples will be packaged and delivered from HAL, [name] to the ABS laboratory by a contracted courier insured to handle medical samples (a trial-specific SOP will be followed). The saliva samples being sent will be documented on a log to be cross-checked by ABS laboratories once the samples are received. ABS laboratories will sign for receipt of the saliva samples and confirm receipt with study site. Samples will be kept frozen until analysis.

13.5 Sample Analysis Procedures

13.5.1 The arrangements for sample analysis

Samples will be analysed at the end of the study by ABS Labs (sections above and below describe how the samples will be handled prior to this). Cotinine and anabasine in human saliva samples will be determined using high performance liquid chromatography coupled to tandem mass spectrometry with multiple reaction monitoring (LC-MS/MS) after basification of the saliva and then liquid -liquid extraction with dichloromethane using cotinine d₃ and

anabasine d_4 as the internal standards. The analysis will be performed over 1 to 600ng/mL for cotinine and 0.1 to 10 ng/mL calibration range for anabasine.

13.5.2 Sample Storage Procedures

Prior to analysis, samples will be stored frozen in ABS Laboratories as per standard operating procedures If a participant withdraws their consent and explicitly states that they do not wish for their data collected thus far to be used, the sample will be destroyed by ABS Laboratories Ltd. without analysing it.

13.6 Sample and Data Recording/Reporting

Data will be pseudo anonymised and only contain a participant ID number. Data will be reported as per the analysis plan.

13.7 Processes at the end of study

All samples will be analysed prior to the End of study notification. Once analysed and the data has been received and reviewed, the samples will be destroyed by ABS Laboratories Ltd

14.0 Trial Medication

14.1 Name and description of investigational medicinal product(s)

Nicorette Invisi (also known as NicAssist Translucent) 10mg and 15mg/16 hours Transdermal Patch.

Description: Semi-transparent, beige, imprinted 13.5 cm2 (15mg) or 9 cm2 (10mg) rectangular TTS with rounded corners. Centrally located on a rectangular, aluminized and siliconized release liner.

Note: The e-cigarette (EC) is not as an IMP in this study as it is a consumer product regulated under the Tobacco Products Directive. We will be providing an EC starter pack to participants (see intervention details), but they will be encouraged to purchase a different EC and/or e-liquid if the one provided does not work for them. This is the current approach by stop-smoking services (e.g. Leicestershire, Bristol and the City of London SSS) who provide EC starter packs as part of standard care and encourage clients to switch to other EC products if needed.

14.2 Legal status of the drug

Nicorette Invisi patches are a licensed product in the UK, and licensed for use in pregnancy with the following indication;

Nicorette Invisi Patch relieves and/or prevents craving and nicotine withdrawal symptoms associated with tobacco dependence. It is indicated to aid smokers wishing to quit or reduce prior to quitting, to assist smokers who are unwilling or unable to smoke, and as a safer alternative to smoking for smokers and those around them.

15mg - PL 15513/0160 10mg - PL 15513/0160

14.3 Summary of Product Characteristics (SmPC)

Please see Nicorette Invisi 15mg patch/NicAssist Translucent 15mg Patch for a summary of Product Characteristics that will be used for the trial (version: 25 May 2016). If an update to this version occurs during the trial, the amendments will be reviewed and if of significance to the safety or integrity of the trial, action will be taken to amend the protocol and study procedures as required.

14.4 Drug storage and supply

IMP will be stored securely at the Health and Lifestyle Research Unit (HAL), [name]. The IMP is to be stored below 25 degree Celsius in line with the manufactures guidance. A week-day temperature log will be kept.

The IMP will be supplied once participants have been randomised. This will be dispatched via Royal Mail recorded delivery, as is standard in some SSS who provide NRT on direct supply (as opposed to prescription). The IMP will not be temperature-regulated during transportation as this is not standard protocol in the SSS.

14.5 Supplier N/A

14.6 Manufacturer

McNeil Products Ltd. [name].

14.7 How the drug should be stored

The IMP will be stored as per manufacturer requirements. The SmPC states that the drug should not be stored above 25 degrees Celsius, and should be stored out of reach and sight of children and animals.

14.8 Details of accountability

Receipt: Upon receipt of the medication at HAL, a member of the study team will sign for the delivery and check contents. If there are any discrepancies, the study team will alert the suppliers. This will be recorded on the accountability log. The temperature in the storage area will be logged on arrival.

Supply: When a pack of medication is to be dispensed to a participant, the date of posting and the participant ID number will be recorded on a log along with the quantity and strength of medication dispensed.

Receipt by participant: Once the participant has received the medication, confirmation and date of receipt will be recorded on the log.

14.9 Medication destruction/return and Recall

There is no requirement for participants to return used packaging or unused IMP any destruction will be undertaken as per the manufactures instruction.

The study team will sign up to recall alerts via the MHRA. In the event of a recall, the research team will review the accountability logs for stock held at the HAL and IMP supplied, and any affected stock will be quarantined and the sponsor informed. If subjects have supply of the affected products they will be contacted to cease use of the IMP.

14.10 Prescription of IMP / Placebo/NIMP

N/A

14.11 Preparation and labelling of IMP

The nicotine patch will be used on-label and as per the packaging instructions, no trial-specific labelling or preparation of the IMP is required.

14.12 Preparation and Administration of IMP

No trial-specific preparation is required.

Participants will self-administer the product with telephone support from the study team: Participants will be advised over the phone that from their TQD the patch is put on as soon as they wake and removed before going to sleep. The following day a new patch will be placed in an area different to the day before to minimise adverse skin reaction. Participants will be advised to place anywhere they feel comfortable and also secure i.e. upper arms, thighs, back.

14.13 Dosage schedules

Participants will be asked to use one patch per day for up to 8 weeks, as is usual in the stop-smoking services. Participants will be asked to report on their patch use at each follow up call.

14.14 Dosage modifications

If participants report that they feel the patch is too strong, i.e. they experience discomfort or nausea, they will receive a lower strength patch (see dosing schedule below).

Dosing Schedule:

Starting strength:	15mg (one patch per day)
Reduced strength:	10mg (one patch per day)

14.15 Known drug reactions and interaction with other therapies

Nicorette Invisi Patch may cause adverse reactions similar to those associated with nicotine given by other means, including smoking, and these are mainly dose-dependent. At recommended doses Nicorette Invisi Patch has not been found to cause any serious adverse effects. Excessive use of Nicorette Invisi Patch by those who have not been in the habit of inhaling tobacco smoke could possibly lead to nausea, faintness or headaches.

14.16 Prior and Concomitant medication

No clinically relevant interactions between nicotine replacement therapy and other drugs have definitely been established.

14.17 Trial restrictions

N/A

14.18 Assessment of compliance

Compliance will be assessed by asking participants each week on how many days they used their nicotine patch. Treatment adherence is a secondary outcome of the trial, and as such non-compliance will not lead to participants being withdrawn from the study or any follow-up procedures.

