4.0 Trial Summary

Full title	Helping pregnant smokers quit: Multi-centre RCT of electronic cigarettes and nicotine patches
Short title and/or Acronym	PREP
Trial Design Methodology	Randomised controlled trial
Phase of the Trial	IV
Study Duration	48 Months: 8m for trial set up; 26m for recruitment; 10m to complete remaining treatment and follow-ups (follow-up time-point after 4-week treatment will vary between 5 months-8 months + 1 month to allow follow up of non-responders); 4m for analysis and close-out.
	Expected start date is 1/5/2017. The planned end date of all clinical interventions is 30/5/2020. The planned end date of the whole trial is 30/4/2021.
Study setting	Recruitment: Multi-site – NHS Trial Co-ordinating centre: Health and Lifestyle Research Unit (HAL), QMUL.
Investigational Medicinal Product(s)	Nicotine Transdermal Patches
Medical condition or disease under investigation	Smoking/tobacco addiction
Planned Sample Size	1140
(Maximum) Treatment duration	8 weeks (4 weeks behavioural support + EC/NRT, and 4 further weeks of EC/NRT if requested).
Follow up duration	3 months post-partum
End of Trial definition	The study would be completed and the REC informed, 6 months after the final participant has been followed up for their 3m post-partum follow-up, to allow for saliva sample analysis to be completed.

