10.3.2 Secondary Endpoints

Changes in smoke intake and in nicotine intake indexed by salivary anabasine and salivary cotinine levels, assessed for participants still using NRT or EC at end of pregnancy and for 'dual users' or those who have reduced their smoking by 50% or more; 7-day point-prevalence abstinence self-reported at 4 weeks, end of pregnancy and at 3 months post-partum; self-reported prolonged abstinence at end of pregnancy and 3 months post-partum; use of NRT and EC throughout pregnancy; proportion of participants reporting adverse events and serious adverse events in each group; proportion of participants in each group reporting adverse events and serious adverse events for themselves or their infant at 3 months post-partum; birth and maternal outcomes.

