Electronic cigarette: The study will use a TPD-approved refillable EC (Innokin Endura T18; TPD product ID: 00132-16-00001) with a tobacco flavoured e-liquid with nicotine content of 18mg (fruit flavour e-liquid will be offered in cases where participants dislike the tobacco flavour). EC are a consumer product and this is an open label trial and so there are no special labelling or packaging requirements. Each person will be dispensed the starter kit with an initial supply of e-liquid and offered further supplies over the phone for up to 8 weeks. Supplies will be sent via recorded delivery.

Dose modifications: Participants who find their products too strong will be offered 10mg nicotine patches or 11mg eliquid.

Weekly phone calls:

Participants will receive guidance on using their allocated product and support in preparation for the Target Quit Date (TQD), on the TQD, and weekly for four weeks thereafter (6 calls in total). The schedule and content of calls will follow the established protocols of pro-active telephone counselling for smokers (e.g. [44]). This support addresses issues such as planning for the quit day and how to deal with difficult situations, such as others smoking around the quitter. We will also collect smoking status and monitor use of EC and NRT and any other stop smoking medications, and adverse events. Study staff will also complete the study questionnaires with the participants.

End of pregnancy phone call (35 week gestation to ten weeks post-partum)

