12.8.2 Schedule of Assessment (in Diagramatic Format)

	Study session									
Measures/ Procedures	Baseline	Pre TQD	TQD	TQD+1 week	TQD+2 weeks	TQD+3 weeks	TQD+4 weeks	TQD+6 weeks	Birth FU	3 month post birth FU
Informed consent + screening	Х									
Baseline questionnaire	Х									
Randomisation	Х									
Saliva sample	Х								Х	
Smoking status/CPD	Х			Х	X	X	X		Х	X
Adverse events				Х	X	X	X		Х	X
EC/NRT use				Х	X	X	X		Х	X
EC/NRT demonstration	Х									
Birth + maternal outcomes									Х	
Behavioural support		Χ	Χ	Χ	X	X	X			
Supply of EC/patches		Χ			X		X	X		

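### Product is supplied for up to 8 weeks, but no adverse-event or product-use collection is scheduled between TQD+4 weeks and the end-of-pregnancy call, so weeks 5 to 8 rest on recall

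*Protocol*

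**What the plan says.** **Length of treatment.** Section 4.0 gives the maximum duration as "8 weeks (4 weeks behavioural support + EC/NRT, and 4 further weeks of EC/NRT if requested"). Section 14.13 says "Participants will be asked to use one patch per day for up to 8 weeks", and 14.12 starts patch use at the quit date: "from their TQD the patch is put on as soon as they wake and removed before going to sleep". For e-cigarettes, 12.8.1 sets the same limit, counted in weeks: "Each person will be dispensed the starter kit with an initial supply of e-liquid and offered further supplies over the phone for up to 8". Section 14.19 speaks of an 8-week patch supply without the on-request condition.

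**Contacts.** Section 12.8.1 puts the support calls before the TQD, "on the TQD, and weekly for four weeks thereafter (6 calls in total"). These calls collect smoking status, product use and adverse events. The table in 12.8.2 marks the adverse-event and EC/NRT-use rows at TQD+1, +2, +3 and +4 weeks, then at the birth follow-up and 3 months after birth. The only row marked at TQD+6 is supply, and there is no week-8 column.

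**What the data are meant to cover.** Section 10.3.2 lists as secondary endpoints "use of NRT and EC throughout pregnancy; proportion of participants reporting adverse events and serious adverse events in each group". Section 10.5 sets adverse events over the whole intervention period as the safety endpoint and includes the number of days used in the adherence measure. Section 14.18 says "Compliance will be assessed by asking participants each week on how many days they used their nicotine patch".

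**The concern.** Comparative safety and adherence are both secondary objectives (10.2). A woman who takes the full course uses product for up to four weeks after the last scheduled question about it. The expected reactions listed in 15.4 are mostly minor: skin irritation, nausea, headache, dizziness, cough, throat irritation. Such events, and a count of days of use, are hard to recall accurately months later, possibly after a birth.

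If the schedule is followed exactly, the second half of a full course is recorded less well than the first half. An analysis plan cannot repair this, because it cannot recover data that were never scheduled for collection.

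**Working it through.** **Inputs from the protocol**
- Gestation at entry: 12 to 24 weeks (11.1).
- Last support call: TQD+4 weeks (12.8.1).
- Next data call: from 35 weeks' gestation to 10 weeks post-partum (12.8.4).
- Course of up to 8 weeks, counted from the TQD (14.12 and 14.13 for patches; taken to be the same for e-cigarettes). The four supply marks in 12.8.2 (pre-TQD, TQD+2, +4, +6), read as two weeks each, also give 4 × 2 = 8 weeks.

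**Assumptions, not fixed in the protocol**
- TQD falls 1 to 2 weeks after randomisation (0 to 3 weeks shown for range).
- Birth at 40 weeks, so 10 weeks post-partum is week 50 and 3 months post-partum is about week 53.

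**Step 1: reproduce the plan's own figure.** Section 4.0 puts follow-up after the 4-week treatment at 5 to 8 months, plus 1 month for non-responders. With 4.35 weeks per month:
- TQD 1 week after randomisation: TQD+4 falls at week 12 + 1 + 4 = 17 or 24 + 1 + 4 = 29. (53 − 17)/4.35 = 8.3 months; (53 − 29)/4.35 = 5.5 months.
- TQD 2 weeks after randomisation: TQD+4 falls at week 18 or 30. (53 − 18)/4.35 = 8.0 months; (53 − 30)/4.35 = 5.3 months.

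The stated 5 to 8 months is reproduced, so the timeline matches the one the protocol uses.

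**Step 2: gap from TQD+4 to the next call.** Earliest call = 35 − (entry + offset + 4); latest call = 50 − (entry + offset + 4).

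| TQD offset (weeks) | Entry (weeks) | TQD+4 at | To week 35 | To week 50 |
|---|---|---|---|---|
| 1 | 12 | 17 | 18 | 33 |
| 1 | 24 | 29 | 6 | 21 |
| 2 | 12 | 18 | 17 | 32 |
| 2 | 24 | 30 | 5 | 20 |

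The range is 5 to 33 weeks. An offset of 0 gives 7 to 34 weeks and an offset of 3 gives 4 to 31.

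**Step 3: gap from the end of a full course (TQD+8).** Subtract 4 weeks: 5 − 4 = 1 to 33 − 4 = 29 weeks.

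**Step 4: share of a full course.** Weeks 5 to 8 are 4 of 8 weeks, or 50% of the maximum course. This applies only to women who go on past week 4.

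**The case against.** Several points on the other side stand.

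- **Recording does not stop at TQD+4.** A reader might infer from the table that later events and use are never recorded. The documents do not support that: both items are collected at the end-of-pregnancy and 3-month calls, 15.4 keeps adverse-event recording open to the end of follow-up, and 14.13 asks for patch use at each follow-up call. The weakness is length of recall.
- **Other routes exist.** Serious events are reported within 24 hours of staff becoming aware (15.7). Birth and maternal outcomes come from hospital records (12.8.1). Patch postings are logged with date, quantity and strength (14.8), and the e-CRF includes product dispensing (18.7). Dispensing is only a proxy for use.
- **Not every woman enters weeks 5 to 8.** It would be wrong to read 50% as the share of all exposure in the trial. Section 4.0 makes these weeks on request, and 8.1 cites an earlier UK trial in which only 7% of women used patches beyond a month.
- **Bias between arms is not shown.** Section 8.1 expects better adherence to e-cigarettes, so a reader might infer that late events are captured differently by arm. The schedule is identical in both arms, and nothing in the protocol describes informal recording at resupply.
- **Women can still report problems.** Further supply is offered by phone, and 14.14 acts on the participant's own report. The protocol does not leave her without contact; it attaches no data collection to that contact.
- **Wording.** The weekly question in 14.18 can be read as one asked at each support call, and the intervention period is not defined; 4.0 itself refers to a 4-week treatment beside an 8-week maximum. This softens the contradiction, but it is also why the sections need reconciling.

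None of this supplies a prospective record of non-serious events or days of use in weeks 5 to 8.

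**Conclusion.** The concern holds in a limited form. For women who use product beyond week 4, the schedule collects no adverse events or use between TQD+4 and the end-of-pregnancy call. That does not fit the safety endpoint in 10.5 or, where use continues, the weekly compliance question in 14.18.

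The delay of 5 to 33 weeks (1 to 29 from TQD+8) is derived, not stated in the protocol, and its upper end pairs the earliest entry with the last permitted contact although calling starts at week 35. The number of women affected cannot be calculated, because the protocol does not estimate how many will request further supply.

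What is at stake is the completeness of non-serious adverse events and adherence in late treatment. The change is worth making, but it does not bear on the validity of the main result.

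**What to change.** 1. In 12.8.2, mark the adverse-event and EC/NRT-use rows at TQD+6. The coordinating team should collect both by a short scripted text or call, in the same way for all women in both arms, whether or not they ask for more product.
2. Add date-anchored questions on use and adverse events in weeks 5 to 8 to the existing end-of-pregnancy call. The TQD+6 contact cannot cover the last two weeks of a full course.
3. Reconcile 4.0, 10.5, 12.8.2 and 14.18 on what the intervention period is and when use is asked about. Include 14.19, which omits the on-request condition. This concerns wording and data collection only; no treatment duration is proposed.

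**Cost.** Step 1 is one brief extra contact per woman. The TQD+6 supply point already exists, but supply in weeks 5 to 8 is on request, so it does not reach everyone. Sections 11.1 and 12.3.3 mention six support calls plus two follow-up calls, so they, and the information sheet where it says the same, would need matching wording. Step 2 needs no extra contact and is the minimum if step 1 is judged too burdensome. Step 3 is text only.

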14.19 Arrangements for post-trial access to IMP and care

Participants will receive 8 weeks supply of patches. Should they require further treatment, they will be referred to their local stop-smoking service or GP.

15 Pharmacovigilance

15.1 General Definitions

Term	Definition
Adverse Event (AE)	Any untoward medical occurrence in a participant to whom a medicinal product has been administered, including occurrences which are not necessarily caused by or related to that product.
Adverse Reaction (AR)	An untoward and unintended response in a participant to an investigational medicinal product which is related to any dose administered to that participant. The phrase "response to an investigational medicinal product" means that a causal relationship between a trial medication and an AE is at least a reasonable possibility, i.e. the relationship cannot be ruled out. All cases judged by either the reporting medically qualified professional or the Sponsor as having a reasonable suspected causal relationship to the trial medication qualify as adverse reactions.
Serious Adverse Event (SAE)	 A serious adverse event is any untoward medical occurrence that: Results in death. Is life-threatening. Requires inpatient hospitalisation or prolongation of existing hospitalisation Results in persistent or significant disability/incapacity. Consists of a congenital anomaly or birth defect. Other 'important medical events' may also be considered serious if they jeopardise the participant or require an intervention to prevent one of the above consequences. NOTE: See 17.6 for events related to underlying pregnancy that will not be reported
Serious Adverse Reaction (SAR)	An adverse event that is both serious and, in the opinion of the reporting Investigator, believed with reasonable probability to be due to one of the trial treatments, based on the information provided.
Suspected Unexpected Serious Adverse Reaction (SUSAR)	A serious adverse reaction, the nature and severity of which is not consistent with the information about the medicinal product in question set out in the Reference Safety Information (RSI): In the case of a product with a marketing authorisation, in the summary of product characteristics (SmPC) for that product. In the case of any other investigational medicinal product, in the investigator's brochure (IB) relating to the trial in question.

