15.2 Site Investigators Assessment

Once participants are randomised into the trial and the local PI confirms eligibility, the participants will be under the care of staff at the trial co-ordinating centre (HAL, QMUL). The local PI at HAL will be responsible for their care (or in his/her absence an authorised medic within the research team) and assessment of any event for:

Seriousness

Assessing whether the event is serious according to the definitions given in section 15.1.

Causality

Assessing the causality of all serious adverse events/reactions in relation to the trial treatment according to the definition given. If the SAE is assessed as having a reasonable causal relationship, then it is defined as a SAR.

Expectedness

Assessing the expectedness of all SARs according to the definition given. If the SAR is unexpected, then it is a SUSAR.

Severity

Assessing the severity of the event according to the following terms and assessments. The intensity of an event should not be confused with the term "serious" which is a regulatory definition based on patient/event outcome criteria.

- o Mild: Some discomfort noted but without disruption of daily life
- Moderate: Discomfort enough to affect/reduce normal activity
- Severe: Complete inability to perform daily activities and lead a normal life

15.3Reference Safety information

The SmPC for the Nicorette Invisi 15mg Patch (section 4.8, version: 25 May 2016) will be used for assessing whether an adverse reaction is expected.

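### Section 15.1 applies a stricter causality test, and names fewer judges, for a serious adverse reaction than for an adverse reaction; 15.2 and 15.8 soften the conflict but do not resolve it

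*Protocol*

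**What the plan says.** The definitions table in Protocol section 15.1 has a row for each class of event.

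- **AR.** The test is that "a causal relationship between a trial medication and an AE is at least a reasonable possibility, i.e. the relationship cannot be ruled out". Either of two parties can make the call: "All cases judged by either the reporting medically qualified professional or the Sponsor as having a reasonable suspected causal relationship to the trial medication".
- **SAR.** The event must be serious and, in the reporting Investigator's opinion, "believed with reasonable probability to be due to one of the trial treatments".
- **SUSAR.** This is a subset of SAR: "A serious adverse reaction, the nature and severity of which is not consistent with the information about the medicinal product in question".

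Section 15.2 has the investigator at the co-ordinating centre assess causality for all serious events. Its rule is: "If the SAE is assessed as having a reasonable causal relationship, then it is defined as a SAR". It tells the assessor to apply the definition given, without naming a row of the table. Expectedness at this step is assessed for SARs only.

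Section 15.8 delegates the Sponsor's medical assessment to the Chief Investigator (CI). The CI or a delegate reviews every SAE within 24 hours of receipt, and the review covers relatedness and expectedness.

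**The concern.** A SAR should be an adverse reaction that is also serious. In 15.1 it is not, because the SAR row changes both the threshold (from possibility to probability) and who decides (from either of two parties to the Investigator). An event can then be serious and meet the AR test yet fall outside SAR, and so outside SUSAR.

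Two consequences depend on the label. In 15.7, day zero for reporting to the MHRA is the day the trials unit is notified of a medically assessed SUSAR. In 27.0, SUSARs go to the DMEC chair with the participant's allocation and cumulative counts by arm, while other SAEs go to DMEC meetings held every 6-12 months. Comparative safety is a secondary objective (10.2) and the trial is open label. Causality calls made with knowledge of the arm should not also depend on which row of a table the assessor reads.

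**Working it through.** No arithmetic applies; the check sets the passages side by side.

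| Place | Causality test | Whose judgement | Product covered |
|---|---|---|---|
| 15.1, AR row | Reasonable possibility, not excluded | Reporting professional or Sponsor | An investigational medicinal product |
| 15.1, SAR row | Reasonable probability | Reporting Investigator | Any trial treatment |
| 15.2, causality step | Reasonable causal relationship, by the definition given | Investigator at the co-ordinating centre | Trial treatment |
| 15.8, CI review | None stated | CI or delegate, for the Sponsor | Not stated |

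**Case 1: a serious event on patch, with a link judged possible but not probable.**
1. Under the AR row, the link cannot be excluded, so the event is an adverse reaction, and it is serious.
2. Under the SAR row, the link is not believed probable, so the event is not a SAR. The SUSAR row then excludes it too.
3. Under 15.2, the phrase used is close to the AR row's closing sentence, which points towards SAR. But 15.2 also sends the assessor back to the definitions, and the definition headed SAR points the other way.
4. Under 15.8, the CI looks at relatedness and expectedness but is given no threshold, so the CI works from the same table.

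The same facts give two defensible classes, and no section says which governs.

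**Case 2: the Investigator judges the event unrelated and the CI judges it possibly related.**
1. Under the AR row, either view suffices, so it is an adverse reaction.
2. Under the SAR row, only the Investigator's opinion is named, so it is not a SAR.
3. Section 15.8 requires the CI's review but does not say that the CI's judgement reclassifies the event.

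**Case 3: a serious event on e-cigarette.** Section 14.1 says the e-cigarette is not an investigational medicinal product, so on its wording the AR row does not reach this event. The SAR row does, because it speaks of the trial treatments. The SAR row is thus stricter on causality but wider on product, which limits how it can be repaired.

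**The case against.** The strongest reply is that the stricter word sits in one table cell and the procedures around it do the real work. Much of this stands.

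- The rule in 15.2 is nearly the AR wording and applies to all serious events.
- Section 15.8 brings the Sponsor's delegate into every SAE, with relatedness and expectedness both in scope.
- Section 15.7 requires reporting of foetal, neonatal, post-neonatal and maternal deaths, stillbirths and non-pregnancy admissions whatever the causality.
- Under 27.0, SAEs that are not SUSARs still reach every DMEC meeting unblinded.

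A reader might infer that possibly related serious events can never be assessed as SUSARs, that the Sponsor's view is ignored for serious events, or that the gravest events escape prompt reporting. The documents support none of these. The expectedness step in 15.2 is limited to SARs, but 15.8 repeats it for all SAEs, and deaths are reportable regardless of the label.

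The reply does not show which threshold applies or who prevails in a disagreement. The timing of the 15.8 safeguard is also not fully secured, because its clock starts at receipt. Section 15.6 exempts listed pregnancy-related and incidental admissions from expedited reporting, while 15.7 says all SAEs are reported within 24 hours. If 15.6 governs, the evident route back to 24-hour reporting for those admissions is the separate SAR rule in 15.7, which depends on the disputed definition.

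**Conclusion.** The point holds as an internal contradiction in the safety definitions. Section 15.1 gives two causality thresholds and two sets of judges, 15.2 adds a third wording, and SUSAR status follows from the stricter row. The practical risk is inconsistent classification of serious events whose link is possible but not probable, or on which the Investigator and the CI differ. It is not wholesale loss of safety signals.

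The size cannot be stated. The documents give no rate for such events, and any count would only restate an assumed rate. The conclusion rests on the ordinary reading that *probable* is a higher bar than *cannot be excluded*, and on no section saying which wording takes precedence. It should be corrected because regulatory timing and prompt notice to the DMEC chair depend on the label.

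**What to change.** Reword the SAR row of 15.1 along these lines: an adverse event that is serious and for which a causal relationship with one of the trial treatments "is at least a reasonable possibility, i.e. the relationship cannot be ruled out", in the judgement of either the reporting investigator or the Sponsor (through the CI as delegate). Use the same threshold in the causality step of 15.2 and the CI review of 15.8, and say in 15.8 that either party's judgement of *related* is enough to make the event a SAR.

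Do not simply define a SAR as an AR that is also serious. The AR row is confined to an investigational medicinal product, so that shortcut would drop reactions to the e-cigarette, which the present SAR row covers.

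The cost is a few lines of protocol wording and a few more SARs to process.
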